1. VERSION HISTORY

Table 1. Summary of Changes

Version/ Date	Associated Protocol Amendment	Rationale	Specific Changes
1/ 03 Mar 2022	7 17 Feb 2022	N/A	N/A
2/ 30 Sep 2022	11 20 Sep 2022	Implemented the changes made in the protocol amendments	
1. Added a primary immunogenicity estimand for model-based GMRs in Section 2.2 and provided more details on its analysis in Section 5.2.2.3 and Section 6.1.2.1.1.2. Updated the seroresponse definition in the footnotes of Table 2.3. Updated the exploratory endpoints in Section 3.3.1.4. Removed the analysis for GMRs of SARS-CoV-2 VOC-neutralizing titers to reference-strain–neutralizing titers in Section 5.2.2.3.5. Added an exploratory immunogenicity estimand for model-based GMRs of neutralizing titers for VOCs not already analyzed as a primary outcome in Section 6.2.6. Removed “confirmed e-diary errors will be excluded from the analysis” in Section 6.1.1.1.1 and Section 6.1.1.2.1.7. Removed the analysis timing of 7 days after study vaccination for the safety and immunogenicity data in Section 7.3.8. Added analysis timing of 3 months after study vaccination for the safety and immunogenicity data in Section 7.3.

2. INTRODUCTION

This SAP provides the detailed methodology for summary and statistical analyses of the data collected in Study C4591031 – Substudy F. This document may modify the plans outlined in the protocol; however, any major modifications of the primary endpoint definition or its analysis will also be reflected in a protocol amendment.

2.1. Modifications to the Analysis Plan Described in the Protocol

Not applicable.

2.2. Study Objectives, Endpoints, and Estimands

The estimands corresponding to each primary, secondary, and exploratory objective in Study C4591031 – Substudy F are described in Table 2 below.

In the primary safety objective evaluations, missing AE start dates will be imputed according to Pfizer safety rules ([Section 5.3](#)). No other missing information (eg, missing e-diary data) will be imputed in the safety analysis.

The estimands to evaluate the immunogenicity objective are based on the evaluable immunogenicity population (see [Section 4](#) for definition). These estimands estimate vaccine effect in the hypothetical setting where participants follow the study schedules and protocol requirements as directed. Missing serology results will not be imputed. Immunogenicity results that are below the LLOQ, denoted as BLQ, will be set to $0.5 \times \text{LLOQ}$ in the analysis; this may be adjusted once additional data on the assay characteristics become available.

Table 2. List of Primary and Exploratory Objectives, Endpoints, and Estimands

Objectives	Estimands	Endpoints
Primary Safety		
To describe the safety and tolerability profile of BNT162b2 (30 µg or 60 µg), BNT162b2 OMI (30 µg or 60 µg), and a combination of BNT162b2 and BNT162b2 OMI (30 µg or 60 µg) given as the fourth dose to BNT162b2-experienced participants	
In participants receiving at least 1 dose of study intervention, the percentage of participants reporting:
 
 Local reactions for up to 7 days following the study vaccination Systemic events for up to 7 days following the study vaccination AEs from the study vaccination through 1 month after the study vaccination SAEs from the study vaccination through 6 months after the study vaccination 	
 Local reactions (pain at the injection site, redness, and swelling) Systemic events (fever, fatigue, headache, chills, vomiting, diarrhea, new or worsened muscle pain, and new or worsened joint pain) AEs SAEs
Primary Immunogenicity		
To describe the immune response to BNT162b2 (30 µg or 60 µg), BNT162b2 OMI (30 µg or 60 µg), and a combination of BNT162b2 and BNT162b2 OMI (30 µg or 60 µg) given as the fourth dose in BNT162b2-experienced participants	
 GMT at each time point GMFRs from before the study vaccination to subsequent time points Percentages of participants with seroresponse^a at each time point GMRs at each time point after the study vaccination between different vaccine groups 	
 SARS-CoV-2 Omicron-neutralizing titers SARS-CoV-2 reference-strain–neutralizing titers
Exploratory		
To describe the immune response to any VOCs not already specified		
 SARS-CoV-2–neutralizing titers for any VOCs not already specified

Table 2. List of Primary and Exploratory Objectives, Endpoints, and Estimands

Objectives	Estimands	Endpoints
To describe the cell-mediated immune response and additional immune response parameters		
• T-cell (by ELISPOT) and B-cell characterization• RBD-binding IgG• RBD-binding IgA
To describe confirmed COVID-19 and severe COVID-19 cases		
• Confirmed COVID-19 cases• Confirmed severe COVID-19 cases• Strain sequencing of COVID-19 cases

a. Seroresponse is defined as achieving a ≥ 4 -fold rise from baseline (before the study vaccination). If the baseline measurement is below the LLOQ, the postvaccination measure of $\geq 4 \times$ LLOQ is considered seroresponse.

2.3. Study Design

This is a randomized, observer-blinded substudy to describe the safety, tolerability, and immunogenicity of high-dose BNT162b2 (60 μ g), high-dose BNT162b2 OMI (60 μ g), and a high-dose combination of BNT162b2 and BNT162b2 OMI at 60 μ g (30 μ g each), given as a single dose. Approximately 180 participants ≥ 60 years of age who have received 3 prior doses of BNT162b2 (30- μ g doses), with the most recent dose being ≥ 4 months prior to randomization, will be enrolled in Israel. Participants will be randomized at a ratio of 1:1:1:1:1 to receive BNT162b2 at 30 μ g, BNT162b2 at 60 μ g, BNT162b2 OMI at 30 μ g, BNT162b2 OMI at 60 μ g, a combination of BNT162b2/BNT162b2 OMI at 30 μ g (15 μ g each), or a combination of BNT162b2/BNT162b2 OMI at 60 μ g (30 μ g each) at Visit 701 as a fourth dose.

Initially, sentinel cohorts (sponsor open-label) of 5 participants per group will be enrolled. An IRC and site representatives will review all reported AEs and reactogenicity e-diary data from the sentinel cohorts collected through Day 7 to allow expanded enrollment of an additional 25 participants per group upon confirmation of an acceptable safety assessment. If the safety assessment is considered not to be acceptable, the protocol may be amended to include a further sentinel cohort employing 50- μ g dose levels of BNT162b2, BNT162b2 OMI, and a combination of BNT162b2/BNT162b2 OMI (25 μ g each).

Table 3 describes the enrollment of the sentinel cohorts and steps to progress to expanded enrollment.

Table 3. Substudy F - Sentinel and Expanded Enrollment

Sentinel Enrollment ^a		
Study Intervention	Number of Participants	Group Number
BNT162b2 30 µg	5	G1
BNT162b2 60 µg	5	G2
BNT162b2 OMI 30 µg	5	G3
BNT162b2 OMI 60 µg	5	G4
Combination BNT162b2/BNT162b2 OMI 30 µg (15 µg each)	5	G5
Combination BNT162b2/BNT162b2 OMI 60 µg (30 µg each)	5	G6

IRC and site representative reviews all reported adverse event and reactogenicity e-diary data from the sentinel cohorts collected through Day 7. Expanded enrollment to commence upon confirmation of an acceptable safety assessment.
--

Expanded Enrollment ^b		
Study Intervention	Number of Participants	Group Number
BNT162b2 30 µg	25	G1
BNT162b2 60 µg	25	G2
BNT162b2 OMI 30 µg	25	G3
Study Intervention	Number of Participants	Group Number
BNT162b2 OMI 60 µg	25	G4
Combination BNT162b2/BNT162b2 OMI 30 µg (15 µg each)	25	G5
Combination BNT162b2/BNT162b2 OMI 60 µg (30 µg each)	25	G6

- Sentinel cohorts will be sponsor open-label.
- If the IRC and site representative's safety assessment is considered not to be acceptable, the protocol may be amended to include a further sentinel cohort employing 50-µg dose levels of BNT162b2, BNT162b2 OMI, and a combination of BNT162b2/BNT162b2 OMI (25 µg each).

3. ENDPOINTS AND BASELINE VARIABLES: DEFINITIONS AND CONVENTIONS

3.1. Primary Endpoint(s)

3.1.1. Primary Safety Endpoints

The primary safety endpoints are as follows:

- Local reactions (redness, swelling, and pain at the injection site) for up to 7 days after the study vaccination.
- Systemic events (fever, fatigue/tiredness, headache, chills, vomiting, diarrhea, new or worsened muscle pain, and new or worsened joint pain) for up to 7 days after the study vaccination.

- AEs from vaccination (received in this study) through 1 month after the study vaccination.
- SAEs from vaccination (received in this study) through 6 months after the study vaccination.

3.1.1.1. Local Reactions

The local reactions assessed and reported in the e-diary are redness, swelling, and pain at the injection site, within 7 days after the study vaccination. This section describes derivations with details for the assessment of local reactions: presence, severity level, duration, and onset day.

Presence or Absence

For each local reaction and any local reaction on any day, Table 4 defines the algorithm to derive the presence of a reaction (yes or no) during the interval within 7 days after the study vaccination.

Table 4. Derived Variables for Presence of Each and Any Local Reaction Within 7 Days for Each Vaccination

Variable	Yes (1)	No (0)
Presence of each local reaction on any day	Participant reports the reaction as “yes” on any day (within 7 days after vaccination).	Participant reports the reaction as “no” on all 7 days (after vaccination) or as a combination of “no” and missing on all 7 days (after vaccination).
Presence of any local reaction on any day	Participant reports any local reaction as “yes” on any day (within 7 days after vaccination).	For all 3 local reactions, participant reports “no” on all 7 days (after vaccination) or a combination of “no” and missing on all 7 days (after vaccination).

Note: Missing e-diary data will not be imputed. Participants with no e-diary data reported will not be included in the e-diary summaries.

Severity and Maximum Severity

Redness and swelling will be measured and recorded in measuring device units (range: 1 to 21) and then categorized during analysis as absent, mild, moderate, or severe based on the grading scale in [Table 5](#). Measuring device units can be converted to centimeters according to the following formula: 1 measuring device unit = 0.5 cm. Pain at the injection site will be assessed by the participant as mild, moderate, or severe according to the grading scale in Table 5.

Table 5. Local Reaction Grading Scale

Local Reaction	Mild (Grade 1)	Moderate (Grade 2)	Severe (Grade 3)	Potentially Life-Threatening (Grade 4) ^a
Pain at the injection site	Does not interfere with activity	Interferes with activity	Prevents daily activity	Emergency room visit or hospitalization for severe pain
Redness	>2.0 cm to 5.0 cm (5 to 10 measuring device units)	>5.0 cm to 10.0 cm (11 to 20 measuring device units)	>10 cm (\geq 21 measuring device units)	Necrosis or exfoliative dermatitis
Swelling	>2.0 cm to 5.0 cm (5 to 10 measuring device units)	>5.0 cm to 10.0 cm (11 to 20 measuring device units)	>10 cm (\geq 21 measuring device units)	Necrosis

a. Only an investigator or medically qualified person is able to classify a reaction as Grade 4; therefore, a confirmed Grade 4 reaction should be reported as an AE in the case report form.

If a Grade 3 local reaction is reported in the reactogenicity e-diary, a telephone contact should occur to ascertain further details and determine whether a site visit is clinically indicated. Only an investigator or medically qualified person is able to classify a participant's local reaction as Grade 4. If a participant experiences a confirmed Grade 4 local reaction, the investigator must immediately notify the sponsor.

For each local reaction after each vaccination, the maximum severity grade will be derived for the e-diary collection period (within 7 days after vaccination) as follows:

Maximum severity grade = highest grade (maximum severity) within 7 days after vaccination among the severity grades reported for that local reaction in the e-diary.

Duration (First to Last Day Reported)

The duration (days) of each local reaction will be calculated as the number of days from the start of the first reported reaction to the resolution of the last reported reaction, inclusive. Resolution is defined as the last day on which the reaction is recorded in the e-diary if the reaction lasts 7 days or less, or the day the reaction ends if it persists beyond the end of the reactogenicity e-diary period following vaccination (the latter will be collected on the CRF). If there is no known date when the reaction ended, then duration will be missing (unknown). Participants with no reported reaction have no duration.

Onset Day

The onset day of each local reaction will be derived. Onset day is defined as the first day of reporting the reaction with any severity after vaccination.

For the onset day of each local reaction, if participants report a change in severity of the local reaction, only the first day of reporting that specific local reaction will be counted.

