3.1.1.2. Systemic Events (Systemic Event Symptoms and Fever)

The systemic events assessed and recorded in the e-diary are fever, fatigue/tiredness, headache, chills, vomiting, diarrhea, new or worsened muscle pain, and new or worsened joint pain within 7 days after vaccination. The derivations for systemic events will be handled similarly to the way local reactions are handled for presence of event, severity level, duration, and onset day (see [Section 3.1.1.1](#)).

The systemic events will be assessed by the participant as mild, moderate, or severe according to the grading scale in Table 6.

If a Grade 3 systemic event is reported in the reactogenicity e-diary, a telephone contact should occur to ascertain further details and determine whether a site visit is clinically indicated. Only an investigator or medically qualified person is able to classify a participant's systemic event as Grade 4. If a participant experiences a confirmed Grade 4 systemic event, the investigator must immediately notify the sponsor.

Table 6. Systemic Event Grading Scale

Systemic Event	Mild (Grade 1)	Moderate (Grade 2)	Severe (Grade 3)	Potentially Life-Threatening (Grade 4)
Vomiting	1-2 times in 24 hours	>2 times in 24 hours	Requires IV hydration	Emergency room visit or hospitalization for hypotensive shock
Diarrhea	2 to 3 loose stools in 24 hours	4 to 5 loose stools in 24 hours	6 or more loose stools in 24 hours	Emergency room visit or hospitalization for severe diarrhea
Headache	Does not interfere with activity	Some interference with activity	Prevents daily routine activity	Emergency room visit or hospitalization for severe headache
Fatigue/tiredness	Does not interfere with activity	Some interference with activity	Prevents daily routine activity	Emergency room visit or hospitalization for severe fatigue
Chills	Does not interfere with activity	Some interference with activity	Prevents daily routine activity	Emergency room visit or hospitalization for severe chills
New or worsened muscle pain	Does not interfere with activity	Some interference with activity	Prevents daily routine activity	Emergency room visit or hospitalization for severe new or worsened muscle pain
New or worsened joint pain	Does not interfere with activity	Some interference with activity	Prevents daily routine activity	Emergency room visit or hospitalization for severe new or worsened joint pain

Abbreviation: IV = intravenous.

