6. ANALYSES AND SUMMARIES

6.1. Primary Endpoint(s)

6.1.1. Primary Safety Endpoints

6.1.1.1. Local Reactions

6.1.1.1.1. Main Analysis

- Estimand: The percentage of participants reporting local reactions (redness, swelling, and pain at the injection site) for up to 7 days after the study vaccination ([Section 2.2](#)).
- Analysis set: Safety population ([Section 4](#)).
- Analysis time point: Up to 7 days after the study vaccination.
- Analysis methodology: Descriptive statistics ([Section 5.2.1](#)).
- Intercurrent events and missing data: The participants without any e-diary data throughout the 7 days after vaccination will be excluded from the analysis; missing values will not be imputed.
- Reporting results: Descriptive statistics for each and any local reaction after the study vaccination in each vaccine group will be presented by maximum severity and cumulatively across severity levels. Descriptive summary statistics will include counts and percentages of participants with the indicated endpoint and the associated 2-sided Clopper-Pearson 95% CIs.

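### Maximum severity is derived from e-diary grades alone, so an investigator-confirmed Grade 4 reaction would show as Grade 3 or lower in the reactogenicity severity tables and bar charts

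*SAP*

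**What the plan says.** SAP Section 3.1.1.1 sets out how local reactions are graded:

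- Redness and swelling are recorded in device units ("range: 1 to 21) and then categorized during analysis as absent, mild, moderate, or severe").
- "Pain at the injection site will be assessed by the participant as mild, moderate, or severe".
- Table 5 has a fourth column, Grade 4, for pain, redness and swelling. Its footnote reserves that grade for an investigator or medically qualified person and adds that "a confirmed Grade 4 reaction should be reported as an AE in the case report form".
- Maximum severity is the "highest grade (maximum severity) within 7 days after vaccination among the severity grades reported for that local reaction in the e-diary".

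Section 3.1.1.2 carries this over to systemic events: "The derivations for systemic events will be handled similarly to the way local reactions are handled for presence of event, severity level". Participants again rate mild, moderate or severe, and Table 6 again defines a Grade 4. Fever is handled separately, by recorded temperature, in Table 7.

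In Section 6.1.1.1.1 the local-reaction results "will be presented by maximum severity and cumulatively across severity levels". Section 6.1.1.2.1 does the same for systemic events, and the bar charts are also divided by maximum severity.

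**The concern.** The grading tables recognise a grade that the derived variable cannot take. Suppose a reaction is confirmed as Grade 4. The participant's diary still holds a lower grade, and the rule reads only the diary. The severity tables and figures would then place the most serious solicited reaction in the trial in the severe category or below, with nothing to tell the reader that it was upgraded.

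The first primary objective is to describe safety and tolerability at 30 µg and 60 µg. Section 5.1 plans no hypothesis tests, so the descriptive tables are themselves the result. A reader comparing severity between dose levels would have to find the event among the AEs, which are summarised by system organ class and preferred term. The SAP specifies no link from there back to the solicited reaction.

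**Working it through.** The SAP states no figure for this point, so the check has two parts: which grades the rule can produce, and how much one event would matter.

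**1. Grades that can be reached**

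Inputs, all from Section 3.1.1.1: device range 1 to 21 units; "1 measuring device unit = 0.5 cm"; Table 5 cut-offs.

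| Device units | Size (units × 0.5 cm) | Grade |
|---|---|---|
| 1 to 4 | 0.5 to 2.0 cm | below Grade 1 |
| 5 to 10 | 2.5 to 5.0 cm | 1 |
| 11 to 20 | 5.5 to 10.0 cm | 2 |
| 21 | 10.5 cm | 3 |

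The top reading is Grade 3. Grade 4 redness is necrosis or exfoliative dermatitis and Grade 4 swelling is necrosis. Neither is a size, so no device reading can give it. The pain rating stops at severe, which is Grade 3. The maximum of values from 0 to 3 cannot be 4.

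A necrotic reaction measuring fewer than 5 units would not reach even Grade 1 under this rule.

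**2. Systemic events**

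The Table 6 events have the same three participant levels and inherit the same derivation, so the same result follows. Fever differs: Table 7 has a category above 40.0 °C that is filled from the recorded temperature.

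**3. Where the CRF enters**

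The same section already uses the CRF to complete a diary variable. When a reaction outlasts the diary period, its end date for the duration calculation comes from the CRF. No matching sentence exists for severity.

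**4. Size of one event**

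Inputs: 5 sentinel plus 25 expanded participants per group (Section 2.3), so n = 30; 6 × 30 = 180 agrees with the stated total. The interval is Clopper-Pearson (Section 5.2.1). One confirmed Grade 4 event is assumed, with e-diary data for all 30.

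- Estimate: 1/30 = 3.3%.
- Lower limit: 1 − 0.975^(1/30) = 0.08%.
- Upper limit: 97.5th percentile of Beta(2, 29) = 17.2%.
- If a Grade 4 row were printed under the present rule: 0/30 = 0%, upper limit 1 − 0.025^(1/30) = 11.6%.

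**The case against.** The strongest reply is that the routing is deliberate. Participants grade what they can judge and qualified staff confirm Grade 4; "therefore, a confirmed Grade 4 reaction should be reported as an AE in the case report form". AEs are themselves a primary safety endpoint, severe AEs are summarised by vaccine group (Section 6.1.1.3.2), and SAEs are both summarised and listed. Keeping diary and investigator data apart is a legitimate reporting choice. That stands as far as it goes: the event is reported. It does not explain why outputs labelled maximum severity should show a grade known to be too low, without a note.

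Four stronger readings are tempting, and the SAP does not support them:

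- **A Grade 4 reaction would vanish.** It would not. Local reactions go to the AE data under the Table 5 footnote. Table 6 has no such footnote, so the SAP does not itself say where a Grade 4 systemic event is recorded.
- **The sentinel review would be misled.** Section 2.3 gives the IRC all reported AEs as well as diary data, Sections 6.1.1.3.2 and 6.1.1.4.2 provide 7-day AE and SAE summaries, and a confirmed Grade 4 is notified to the sponsor immediately.
- **The tables will print a Grade 4 row reading 0/30.** The SAP does not say that there is such a row, and table shells are not at hand.
- **The primary percentages are wrong.** The estimand is the percentage reporting a reaction at all. If the diary recorded the reaction at any grade, that percentage is unchanged.

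It is also fair to say that no rate of Grade 4 events is given and that such events are likely to be rare.

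**Conclusion.** The point holds, within limits. Followed as written, Section 3.1.1.1 cannot produce a maximum severity of Grade 4, so a confirmed Grade 4 local reaction or Table 6 systemic event is under-graded in the severity split of the reactogenicity tables and bar charts. Fever is unaffected, and AE reporting and the sentinel review are not compromised.

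One event in a group of 30 is 3.3% (95% CI 0.1 to 17.2) that would not be shown as Grade 4. With no such event, nothing changes.

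The conclusion rests on one inference. The SAP does not say outright that Grade 4 cannot be entered in the diary; it follows from the three participant levels, the device range and the investigator-only classification. The change is worth making because it is cheap and the severity profile belongs to a primary objective.

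**What to change.** Redefine maximum severity in Section 3.1.1.1 as the higher of:

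(a) the highest e-diary grade within 7 days after vaccination; and
(b) Grade 4, where the investigator confirmed a Grade 4 event for that solicited reaction with onset within 7 days, as recorded on the CRF.

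State its limits in the same place:

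- Apply it to local reactions and the Table 6 systemic events, not to fever.
- Leave out symptoms that Section 3.1.1.2 directs to be recorded as AEs because of a positive SARS-CoV-2 test. Otherwise the merge would bring them back as reactogenicity.
- Keep the e-diary denominator. Sections 6.1.1.1.1 and 6.1.1.2.1 exclude participants with no diary data, so list any Grade 4 event in such a participant separately.
- For Table 6 events, name the CRF source, since only Table 5 has the recording footnote.
- Say how the Table 4 presence variable is set if the diary holds no report of that reaction, so that the severity rows still add up.
- Footnote the tables and bar charts to say that the event also appears in the AE tables.

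The cost is a few sentences of SAP text and one merge of CRF and diary data. The small downside is that the event appears in two sets of tables, which the footnote covers.
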